PROTOCOL TITLE:

1) Protocol Title Effects of blood flow restriction rehabilitation after bone patellar tendon bone anterior cruciate ligament reconstruction

2) Investigator [name]

3) Objectives

Athletes commonly experience a significant amount of muscular atrophy following ACL reconstruction surgery associated with an increased risk of re-injury and an increase in time of recovery and return to sport participation. A combination of low intensity resistance exercise and blood flow restriction (BFR) therapy has been shown to elicit responses similar to high intensity resistance exercise with regards to reduced risk. We hypothesize that chronic low intensity resistance exercise combined with BFR will improve muscular strength, reduce skeletal muscle atrophy, and will enhance recovery. Therefore, the specific aims of this study are as follows:

1. Determine if BFR added to standard post-operative rehab will prevent skeletal muscle atrophy and promote skeletal muscle growth during 12-weeks of rehab training compared to traditional rehab alone. The working hypothesis, founded on previous literature, is that

combined rehab and BFR will enhance skeletal muscle growth and prevent atrophy to a greater extent than rehab alone.

2. Determine if BFR added to standard post-operative rehab will improve muscular strength following surgery compared to traditional rehab alone. Because strength can be attributed to skeletal muscle mass, the working hypothesis, founded on previous literature, is that combined rehab and BFR will enhance skeletal muscle strength and fatigue resistance to a greater extent than rehab alone.

3. Determine if BFR added to standard post-operative rehab will improve functional outcomes following surgery compared to traditional rehab alone. The working hypothesis, founded on previous literature is that BFR will improve functional outcomes over rehab alone.

The expected outcome of the proposed work is the identification of a novel therapy that can overcome muscle atrophy and decrease recovery time following surgery. The findings of the proposed study will have a positive impact, because they will allow us to translate this information into evidence-based clinical interventions to improve functional outcomes with reductions in risk during rehab and upon returning to sport participation.

4) Background

Athletes who undergo ACL reconstruction are known to experience quadriceps atrophy with resulting decreased strength in their injured extremity. This is likely due to their inactivity following injury and also to disuse atrophy during initial post-operative period. It has been

shown that some patients may continue to have atrophy even 9 years post ACL reconstruction [1]. As a result, there is an increased risk of re-injury and an extended timeline for recovery and return to athletic participation. Current intensive rehabilitation programs accelerate return to play timelines, however, the initial quadriceps atrophy prior to beginning formal rehabilitation is still not addressed. Therefore, the need for more effective rehabilitation methods is of great interest to clinicians and physical therapists.

Blood flow restriction (BFR) exercise training, has been shown to induce skeletal muscle hypertrophy (growth) even when using low resistance loads (<30% One-repetition maximum). It has also been shown that BFR significantly improves fatigue resistance and greater strength gains compared to traditional resistance training alone [6,7]. In a recent study involving Division IA athletes, low resistance BFR training was shown to increase strength and muscle size as compared with traditional high resistance training in as little as four weeks [8]. Strikingly, blood flow restriction alone has been observed to decrease atrophy of the quadriceps following ACL reconstruction [10]. Thus, this type of training may be promising for ACL reconstruction patients who are unable to partake in heavy weight training post-operatively.

While the mechanisms that promote recovery and an increase in skeletal muscle hypertrophy are not well understood, it has been hypothesized that BFR elicits a stress response associated with decreases in intramuscular pH, accumulation of metabolites, increases in the ratio of carbon dioxide to oxygen, and changes in osmotic pressure [11]. In laymen's terms, these effects are similar to high volume / high intensity exercise but achieved with minimal resistance and reduced risk to the patient following surgery. Similar to high intensity resistance exercise, BFR exercise with low resistance levels elicits significant elevations in protein synthesis and associated changes in anabolic signaling within skeletal muscle cells (14). Encouragingly, BFR exercise does not show increase in markers for muscle damage such as myoglobin or creatine kinase [2].

Much effort has been made to optimize BFR training in terms of optimal cuff size, occlusion pressures, and training weight or resistance. Scott et al have provided a guideline for BFR therapy [18]. The generally agreed upon low resistance weight amount should be 20-30% of the maximum repetition (1RM) for the given exercise [7,18,19]. However, optimal training durations have yet to be determined. Additionally, functional assessments following chronic BFR training and association between changes in leg muscle mass and performance have yet to be thoroughly evaluated. In light of the present literature, we hypothesize that 12 weeks of combined low intensity leg exercise and BFR therapy will mitigate post-operative muscular atrophy, improve muscular strength, and improve functional outcomes in athletes following ACL reconstruction surgery compared to a traditional rehabilitation program in men and women athletes (age 18-35yr).

5) Setting of the Human Research

The study will start for each subject in the clinic setting. Consent for the study will be obtained after explaining all aspects of the study. The subject will undergo their scheduled procedure in the operating room with no differences between the control group and study group. Physical therapy will take place at two locations in Houston, two times per week for 12 weeks.

Questionnaires will be conducted before surgery, prior to physical therapy instructed BFR exercises at week two, two months, six months, and one year post-operatively. Questionnaires will take 20 minutes to complete.

6) Resources available to conduct the Human Research

DEXA (Dual Xray Absorptiometry) Scanner

Automated Electronic Blood Flow Restriction Cuffs (used for physical therapy)

Rehabilitation exercise equipment.

Rehabilitation facility.

7) Study Design

The study will be a prospective randomized control trial consisting of subjects requiring ACL reconstruction with BTB autograft. Subjects will be randomly divided into two groups following their inclusion in the study. One group will undergo the normal ACL rehab protocol as determined by Drs. [name] and [name]. The study group will undergo normal ACL rehab modified by use of a tourniquet for blood flow restriction during selected exercises.

On the day of the procedure, the surgeon will measure the subject's thigh circumference 1/3 distance from the superior pole of the patella to the inguinal crease. The subject will then undergo the normal BTB autograft ACL reconstruction procedure. A subject will be excluded from the study if a meniscal repair is performed. At the subject's two week post-operative clinic visit, the physician will measure thigh circumference at 1/3 distance from the superior pole of the patella to the inguinal crease. Study group subjects will begin physical therapy instructed BFR exercises at two weeks post operatively. Study group subjects will be taken through normal ACL rehab protocol as well as BFR exercises. Control group subjects will do the same exercises and formal physical therapy rehab protocol as the study group without BFR.

The BFR exercises will consist of: bilateral leg press week 3-10, eccentric leg press weeks 4-10, hamstring curl week 4-6, eccentric hamstring curl weeks 7-10, straight leg press weeks 6-10. The pressure used will be elevated to occluded blood flow by 80% (80% occlusion pressure) which will be determined for each individual subject. Subjects will do exercises at 20% of 1RM in 4 sets of 30-15-15-15 repetitions separated by 30 seconds of rest. Repetition maximum (1RM) will be determined by the contralateral leg, using the greatest amount of weight with full range of motion and proper form. This will be done over three separate tries, separated by one minute breaks. Resistance loads will be adjusted every 2 weeks as strength improves. During the exercise protocol, if patients are unable to complete the prescribed amount of repetitions, rest periods between sets will be increased as needed. The control group will do these exercises without BFR. Both study and control groups will also do the surgeons' standard post-ACL reconstruction physical therapy protocol.

Cuff pressures will be determined using the Loenneke et al outline, based off of thigh circumference and estimated cuff pressure for 50% artery occlusion [19].

Body composition (DEXA), bone density (DEXA), IKDC and Tegner Lysholm scores will be recorded at first rehabilitation visit, two weeks, eight weeks and 12 weeks following the initiation of rehab (1 wk following surgery). Y- balance, single leg squat distance, and single leg

step down will be measured at 8 weeks and 12 weeks of rehab. Return to play will be recorded as the number of months after the day of operation until subject returns to sport.

a) Recruitment Methods

Patients will be informed of study after counseled in the clinic on their need for the procedure. Patients will be recruited at the Houston Methodist Hospital by either [name], [name], or [name]. Patients will be asked if they would like to be included in the study before leaving clinic. If the patients agree to participate they will complete all necessary paperwork in the clinic.

b) Inclusion and Exclusion Criteria

Subjects. We will test our central hypothesis in 70 healthy adults (18-35 yr) who are participating in athletics or are recreationally trained. **Exclusion criteria** include subjects that demonstrate any of the following:

- Concomitant meniscal tear or additional ligamentous injury to the knee
- Obesity (BMI>30)
- Diabetes
- Cardiovascular, renal, liver or pulmonary disease
- Active infections
- Cancer (current or treated within the past 2 years) or coagulation disorder
- Rapid weight change within the past year
- Physically unable to participate in the intervention
- Are not currently taking, or recently (w/in 1month of participation) taken prescribed or over the counter ergogenic aids or compounds known to be banned by the NCAA. The NCAA banned substances list can be viewed from:
<http://www.ncaa.org/health-and-safety/policy/2014-15-ncaa-banned-drugs>
- Unable to complete a minimum of 85% of the assigned rehabilitation sessions.

These conditions are excluded as they can impact muscle protein metabolism and training responses which would yield confounding the results.

Criteria for stopping treatment:

-Exorbitant pain (VAS >8/10) related or unrelated to exercise -Numbness, tingling, paresthesias >2 hours following any BFR session -Instability preventing safe, quality exercise -Nausea, severe headache, vomiting, fainting within 2 hours of BFR session

e) Data management

The PI will be responsible for all data collected, its confidential storage, and deletion after the study is completed.

f) Withdrawal of subjects

N/A

8) Risks to subjects

Minimal risks of thigh pain at tourniquet site and deep venous thrombosis. Minimal radiation exposure from DEXA scan measurement. However, the radiation is comparable to participating in a long plane flight. Minimal risk of injury to patients as they will be treated with the current standards of care during rehabilitation under close supervision from the physical therapy team.

9) Potential benefits to subjects

Subjects in the BFR group may experience quicker quadriceps/hamstring strength recovery as well as earlier return to play.

10) Provisions to protect the privacy interests of subjects

PHI information will not be used or published in the study as all information will be used to form aggregate data. The data will be kept on a secure password protected, hospital server and will be deleted after the study is complete.

11) Provisions to maintain the confidentiality of data

See #10

12) Cost to subjects

The cost of a routine clinic visit, ACL reconstruction, and physical therapy sessions will be involved in this study. No additional costs to the patient will be accrued with regards to the additional research portions of the evaluation.

13) Consent process

The subjects will then be asked in private, after explanation of the bone patellar tendon bone autograft ACL reconstruction procedure if they wish to participate in the study. The consent will be read and either accepted/obtained or declined. Participants will also be asked if they are taking oral contraceptives or if they have a history of blood clots or pulmonary embolus in order to determine exclusion for oral contraceptives, blood clots, and pulmonary embolus. The participants will be told that they may opt out of the research study at any time- even after they have signed the consent to participate in the study.

14) Process to document consent in writing

The standard consent form for this project will be explained and if the subject wishes to participate the consent will be signed prior to the patient leaving the clinic on the day a BTB ACL reconstruction is decided upon as the treatment. The PI will explain and obtain the consent for each participant in the study.

References

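### The protocol does not place randomisation after surgery, so randomised subjects can be removed for an intra-operative meniscal decision, and its two meniscal exclusion rules disagree

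*Protocol*

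**What the plan says.** The order of events has to be pieced together from several sections of the protocol.

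- **Inclusion.** Section 7(a): "Patients will be asked if they would like to be included in the study before leaving clinic".
- **Consent.** Section 14: "the consent will be signed prior to the patient leaving the clinic on the day a BTB ACL reconstruction is decided upon".
- **Allocation.** Section 7: "Subjects will be randomly divided into two groups following their inclusion in the study". No date or visit is given.
- **Surgery.** Section 5: "The subject will undergo their scheduled procedure in the operating room with no differences between the control group and study group".
- **Exclusion at surgery.** Section 7, after describing the operation: "A subject will be excluded from the study if a meniscal repair is performed".
- **Listed criterion.** Section 7(b) excludes "Concomitant meniscal tear or additional ligamentous injury to the knee". When and how a tear is to be assessed is not stated.
- **Subjects who leave.** The entry under "f) Withdrawal of subjects" is marked not applicable.

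BFR begins only two weeks after the operation, and section 7 already has a clinic visit at that time. No section describes concealment of the allocation or blinding of the surgeon.

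**The concern.** Eligibility should be settled before allocation. Here one eligibility rule depends on what the surgeon does during the operation, and the text points to allocation having happened by then. Two harms are possible.

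The first is loss of subjects after allocation. A subject excluded from the study would presumably contribute no outcomes, and the protocol has no rule for following, replacing or reporting such subjects. A later analysis could not recover them.

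The second is bias. Performing a repair is the surgeon's decision. If the surgeon knew the arm and this affected the decision, or affected how an unrepaired tear was classified, the subjects left in the two arms would no longer be comparable.

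Separately, the two meniscal rules give different answers for a tear that is found at surgery and not repaired. Section 7(b) puts that subject out and section 7 keeps the subject in. On the natural reading of the timing, that choice also falls after allocation.

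**Working it through.** **Order of events.** Setting the sections in time order gives:

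1. clinic visit, with inclusion and consent (sections 7(a) and 14);
2. randomisation, following inclusion (section 7);
3. surgery, described with both groups named (section 5);
4. exclusion if a repair is performed (section 7);
5. start of BFR at two weeks after surgery (section 7).

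Step 2 is the only one without a time. Its wording ties it to step 1, and nothing ties it to the end of step 3.

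**Inputs for size.** The protocol gives one usable figure, 70 subjects in total. It gives no derivation of that number, no allocation ratio and no meniscal repair rate, so there is no stated figure to reproduce. Everything below assumes that 70 is the number randomised, 35 per arm, with repair rates p of 10%, 20% and 30% for illustration.

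**Loss unrelated to arm.** Subjects left = 70 × (1 − p). Standard error ratio = 1/√(1 − p). For power, 35 per arm with two-sided alpha 0.05 and 80% power (both assumed) detects (1.960 + 0.842) × √(2/35) = 0.67 SD. Power for that same difference is then recalculated with 35 × (1 − p) per arm.

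| p | Subjects left | SE ratio | Power for 0.67 SD |
|---|---|---|---|
| 0% | 70 | 1.000 | 80% |
| 10% | 63 | 1.054 | 76% |
| 20% | 56 | 1.118 | 71% |
| 30% | 49 | 1.195 | 65% |

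Chance imbalance between arms adds almost nothing. At p = 20% the SD of the difference in exclusions is √(2 × 35 × 0.2 × 0.8) = 3.35 subjects. A split of 30 and 26 instead of 28 and 28 changes the standard error by √[(1/30 + 1/26)/(2/28)] = 1.003, about 0.3%.

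**Removal influenced by arm.** Suppose a share t of subjects have a repairable tear and their outcomes are g SD worse.

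- All removed in one arm and none in the other: false difference = t × g.
- All removed in one arm and half in the other: false difference = (t/2) × g/(1 − t/2).

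With t from 20% to 40% and g from 0.25 to 0.5 (all assumed):

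- smallest: 0.1 × 0.25/0.9 = 0.03 SD, two-sided type I error about 5.1%;
- largest: 0.4 × 0.5 = 0.20 SD. With 21 and 35 subjects left, SE = √(1/21 + 1/35) = 0.276, and type I error is about 11%.

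**Tear against repair.** Every repair implies a tear, so the rules agree when a repair is done and when there is no tear. They disagree in one case, the tear left unrepaired.

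**The case against.** A reader might infer that the protocol states that subjects are randomised before surgery and that the surgeon knows the arm. It states neither. Randomisation is never dated, and since one criterion depends on the operation, inclusion could be regarded as complete only afterwards. The section 5 sentence describes what each group receives and does not prove that the groups had been formed. Knowledge of the arm is inferred from silence. These points stand, and they limit the claim to what the text suggests and fails to prevent.

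A reader might also infer that randomisation has been undone. That does not follow. The exclusion occurs about two weeks before BFR starts, so treatment cannot cause it. Bias needs both a known arm and an effect of that knowledge on the decision. Without these, only numbers are lost.

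The illustrative rates are open to challenge too. If tears are screened out before surgery under section 7(b), only missed tears reach the intra-operative rule, and the true rate could be below 10%. The 70 may also mean subjects who stay in the study, and then the table does not apply. Finally, it is tempting to say that later randomisation avoids all these losses. It does not: the same subjects leave, but before allocation.

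The tear and repair rules could work together as a pre-operative screen and a backstop at surgery. The protocol does not say so, and the unrepaired tear would still be unresolved.

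**Conclusion.** The point holds as a weakness in the fixed order of events, and should be corrected. On the natural reading of sections 5, 7, 7(a) and 14, subjects are randomised at or soon after clinic inclusion and can then be removed for an intra-operative decision that could be made with the arm known. No section places allocation later or conceals it.

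The firm part of the harm is loss after allocation. Its size is not known: the 5% to 20% rise in standard errors rests on assumed repair rates of 10% to 30% and on 70 being the number randomised. Bias is possible but not shown. Even the deliberately uneven scenarios above give false differences of 0.03 to 0.20 SD.

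The conflict between the tear rule and the repair rule is explicit in the text and does not depend on when randomisation takes place.

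**What to change.** Keep consent in the clinic, and state that randomisation takes place after surgery, once meniscal status is recorded. The existing two-week visit would serve, after the baseline measurements and before the first BFR session. The arms are treated alike until then, so nothing in the design needs earlier allocation. State whether 70 is counted at randomisation.

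Reconcile the meniscal wording in sections 7 and 7(b) into one criterion, applied before randomisation, that settles how a tear left unrepaired is handled. Which clinical rule to adopt is for the investigators.

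If allocation must stay before surgery, conceal the arm from the surgeon until the operation is complete, and keep and report all randomised subjects by arm.

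The change costs protocol wording and a later allocation step at a visit that already exists. The therapy sites would learn the arm only shortly before the first BFR session. More patients must be consented than randomised if 70 is counted at randomisation: at the assumed rates, 70/0.9 = 78, 70/0.8 = 88 or 70/0.7 = 100, rounded up.

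### Completing 85% of assigned sessions (21 of 24) is written as an exclusion criterion, so randomised subjects can be removed after treatment starts, possibly unequally by arm

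*Protocol*

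**What the plan says.** Section 7 b) of the protocol lists exclusion criteria. The last is "Unable to complete a minimum of 85% of the assigned rehabilitation sessions". The list closes with a reason meant to cover all its items: "These conditions are excluded as they can impact muscle protein metabolism and training responses which would yield confounding the results".

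Section 5 sets the number of sessions: "Physical therapy will take place at two locations in Houston, two times per week for 12 weeks". On timing, Section 14 says that "consent will be signed prior to the patient leaving the clinic" on the day reconstruction is decided upon, and Section 7 says "Subjects will be randomly divided into two groups following their inclusion in the study". No day of randomisation is given, but both steps come before any session could be counted.

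Four criteria for stopping treatment follow the exclusion list. Two are tied to a BFR session: one is "Numbness, tingling, paresthesias >2 hours following any BFR session", and the other covers nausea, severe headache, vomiting or fainting within two hours. Controls do the same exercises without BFR. The last BFR exercises in Section 7 finish at week 10 ("eccentric hamstring curl weeks 7-10, straight leg press weeks 6-10").

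Section 7 f), on withdrawal of subjects, reads only N/A, while Section 13 tells subjects that "they may opt out of the research study at any time- even after they have signed the consent".

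**The concern.** A count of completed sessions exists only during or after treatment. Used as an exclusion, it selects on something the intervention can change, and the groups compared are then no longer the groups that were randomised.

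The loss need not be equal. Only BFR subjects can meet two of the four stopping criteria. If more BFR than control subjects are removed, and those removed would have done worse, the remaining BFR group looks better with no true effect. The protocol's own reason for its exclusions is that they affect training responses, so it gives no ground for treating removal as unrelated to outcome.

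There is also a measurement problem. With withdrawal marked N/A, nothing says that a subject excluded for attendance is still measured at 8 and 12 weeks. Values never collected cannot be restored by any analysis plan.

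**Working it through.** **Threshold, from the protocol's figures.** Sessions: 2 per week × 12 weeks = 24. 0.85 × 24 = 20.4, so 21 are needed (21/24 = 87.5% passes; 20/24 = 83.3% fails). Three sessions may be missed; a fourth excludes.

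**What a BFR stop does, from the text.** BFR exercises end at week 10, which leaves 2 weeks × 2 = 4 sessions. A subject whose attendance ends with a BFR stop has at most 24 − 4 = 20 sessions and always fails, provided the later sessions still count as assigned. A subject who stops BFR but keeps attending loses no sessions. The text does not choose between these.

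**How many could fall below 21 (attendance assumed).** With independent attendance at rate p, the share excluded is P(X ≤ 20), X ~ Binomial(24, p):

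| p | Share excluded | Of an assumed 35 per arm |
|---|---|---|
| 0.95 | 3.0% | 1.0 |
| 0.90 | 21.4% | 7.5 |
| 0.85 | 49.5% | 17.3 |

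**Bias with no true effect (losses and correlation assumed).** Suppose fraction a of controls and b of BFR subjects are removed because they are lowest on a normal variable that has correlation ρ with outcome. The remaining mean rises by ρ·m(f), where m(f) = φ(z_f)/(1 − f) and z_f is the f-quantile of the standard normal. Then

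bias = ρ·[m(b) − m(a)],

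with m(0.10) = 0.195, m(0.15) = 0.274, m(0.20) = 0.350, m(0.30) = 0.497 and m(0.40) = 0.644. The false-positive rate is for a two-sided 5% normal test with SE = √(1/n_control + 1/n_BFR), where n is 35 × (1 − loss) in each arm.

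| Control loss | BFR loss | ρ | Bias (SD) | False-positive rate |
|---|---|---|---|---|
| equal | equal | any | 0 | about 5% |
| any | any | 0 | 0 | about 5% |
| 10% | 20% | 0.3 | 0.3 × (0.350 − 0.195) = 0.046 | 5.4% |
| 10% | 30% | 0.5 | 0.5 × (0.497 − 0.195) = 0.151 | 8.7% |
| 15% | 40% | 0.7 | 0.7 × (0.644 − 0.274) = 0.259 | 14.8% |
| 30% | 10% | 0.5 | −0.151 | 8.7% |

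For the 10% v 30% row: n = 31.5 and 24.5, SE = 0.269, shift = 0.151/0.269 = 0.56 standard errors. The 15% v 40% row is an extreme case; calculations based on the t distribution put its rate between 14.4% and 17.5%.

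**Loss of numbers without bias.** An equal 21% loss takes 70 to about 55 (27.5 per arm). For a two-sample t-test at two-sided 5% and 80% power (all assumed; the protocol states none of these), the detectable difference rises from 0.68 SD at 35 per arm to 0.77 SD.

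**Secondary: losses at surgery.** If allocation precedes surgery, the exclusion for meniscal repair in Section 7 also removes randomised subjects. At an assumed 10% loss (31.5 per arm) the detectable difference is 0.72 SD; at 5% to 20%, it is 0.70 to 0.76 SD.

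**The case against.** The strongest objection is that the item sits in an eligibility list whose other entries can be judged at entry, so it may mean patients who foreseeably cannot attend. That reading is possible. It is the weaker one, because physical inability to take part is already a separate item, no screening assessment of attendance is described, and a precise share of assigned sessions is a count. If the mild reading was intended, the wording still permits the harmful one.

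Second, standard therapy exists independently of the cuff, and nothing says attendance ends when BFR stops; nor is it stated that sessions after such a stop still count as assigned. This stands. Unequal loss is a possibility, and its size cannot be taken from the text.

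Third, the loss rates, correlations and power inputs are assumed, the mildest non-zero case is negligible, and nothing in the protocol links symptoms after a BFR session to lean mass or strength. This also stands: the figures show a range that includes zero and are not a forecast.

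Fourth, the analysis population belongs to a statistical analysis plan, which is not shown. That plan could define an all-randomised analysis, but it would not change whom the protocol excludes or ensure that they are measured. The protocol does not forbid measuring poor attenders, but it does not require it either.

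Fifth, the surgery-related points are separate and minor. Surgery is the same in both arms, so that exclusion mainly costs numbers, and the two meniscal rules could apply at successive stages. The main point does not depend on them.

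**Conclusion.** The concern holds. As written, the protocol makes a post-randomisation count, 21 of 24 sessions, a ground for exclusion, and it has a route by which only the BFR arm can lose subjects. The threshold and the limit of 20 of 24 after a BFR stop that ends attendance follow from the text, the latter if later sessions still count as assigned.

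The size of any bias rests on assumptions: none if losses are equal or unrelated to outcome, 0.05 to 0.15 SD in the moderate cases, and 0.26 SD in the extreme one, with the sign reversed if controls lose more. Even without bias, numbers are lost.

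This must be corrected, because it undermines the comparability that randomisation provides and because missed 8- and 12-week measurements cannot be recovered. The points on randomisation day and meniscal tears are secondary and conditional.

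**What to change.** - In Section 7 b), replace the 85% item with one judged before randomisation: the subject is willing and expected to attend the sessions.
- State that all randomised subjects are measured at the planned visits and analysed in their assigned group, whatever their attendance and whether or not BFR was stopped. Report those who completed at least 85% only as a sensitivity analysis.
- In Section 7 f), replace N/A with text that matches this and the opt-out in Section 13.
- Secondary: state when randomisation takes place, after surgery and before the first BFR session; the existing two-week visit would serve. Reconcile the repair rule in Section 7 with the tear criterion in Section 7 b), so that it is clear what happens when a tear is found at surgery and not repaired.

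The cost is protocol wording and fixing the randomisation step at a visit that already exists. The drawback is that non-attenders may slightly dilute the all-randomised estimate; the sensitivity analysis would show the result among attenders.

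### The 85% session criterion does not say whether it means expected attendance at entry or actual attendance; read as actual attendance it would exclude randomised subjects, and 7(f) has no rule to keep them in follow-up

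*Protocol*

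**What the plan says.** Section 7 (Study Design) sets the order of events: "Subjects will be randomly divided into two groups following their inclusion in the study". Section 7(b) then lists the exclusion criteria, and the last of them is "Unable to complete a minimum of 85% of the assigned rehabilitation sessions". The reason given for the whole list is "These conditions are excluded as they can impact muscle protein metabolism and training responses".

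Section 5 sets physical therapy at "two times per week for 12 weeks". Section 7 starts rehabilitation one week after surgery and BFR two weeks after surgery. It schedules DEXA, IKDC and Tegner Lysholm scores at the first rehabilitation visit and at two, eight and 12 weeks of rehabilitation, and functional tests at eight and 12 weeks. None of these assessments is made conditional on attendance.

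Section 7(b) also gives four criteria for stopping treatment, and section 13 lets subjects opt out at any time. Section 7(f), on withdrawal of subjects, contains only N/A.

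**The concern.** A criterion in an eligibility list should be decidable before allocation. This one refers to completing a share of sessions that mostly take place after allocation. If site staff apply it to attendance as it happens, a randomised subject becomes excluded because of something that occurred after randomisation. The comparison would then be between good attenders in each arm and not between the groups that randomisation formed. The protocol's own rationale ties the listed conditions to training response, so removal on this ground would concern something it regards as related to outcome.

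Part of this cannot be repaired at the analysis stage. An analysis plan can define who is analysed, but it cannot supply an eight- or 12-week DEXA scan or functional test that was not done because the subject was treated as excluded. Whether assessments continue is a matter for the protocol, and 7(f) is where one would look for it.

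**Working it through.** **Threshold (from the document).**
- Sessions: 2 per week × 12 weeks = 24 (section 5).
- 0.85 × 24 = 20.4, so 21 sessions are needed (21/24 = 87.5%; 20/24 = 83.3% fails).
- At most 3 sessions may be missed; the fourth miss fails the criterion.

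**When failure can be known (from the document).** BFR starts two weeks after surgery, so allocation must exist by then. Rehabilitation starts one week after surgery, so at two sessions a week about 2 sessions can have taken place. Four misses cannot have been observed by that time. Actual failure is therefore always known after randomisation.

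**Which reading the text supports.**
- For actual attendance: the list is introduced as covering subjects who demonstrate an item, and a separate item already covers physical inability to take part.
- For expected availability: the criterion speaks of being unable, sits in an eligibility list, and inclusion precedes randomisation.
- Neither side settles it.

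**How many subjects could be affected (illustration).** The protocol gives no attendance rate. Assume each session is attended independently with the same probability p for everyone, and let X be the number attended of 24. The share failing is P(X ≤ 20):

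| Assumed p | P(X ≤ 20) | Expected of 70 |
|---|---|---|
| 0.95 | 0.030 | 2.1 |
| 0.925 | 0.101 | 7.1 |
| 0.90 | 0.214 | 15.0 |

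Real attendance is likely to cluster within subjects, so these figures show only that the count is sensitive to p.

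**Loss of precision if those subjects were also left out of the comparison (illustration).** The protocol states 70 subjects but no allocation ratio, error rate, power or effect size, so the sample size cannot be reproduced. Assume equal arms, a two-sided 5% t-test and 80% power. The normal approximation is d = (1.96 + 0.84) × √(2/n per arm), which gives 0.67 SD at 35 per arm. The t-based values are:
- 35 per arm (70): 0.68 SD
- 34 per arm (68): 0.69 SD
- 28 and 27 per arm: 0.76 and 0.78 SD, so about 0.77 SD with 55 in total

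Under the entry reading nobody randomised is removed and both illustrations are zero.

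**The case against.** The strongest reply is that the harmless reading is the natural one. The word is unable, which describes capacity; the line sits under eligibility; and eligibility is settled before randomisation. The separate item on physical inability does not make it redundant, because travel or work schedules can also prevent attendance. Where the protocol does exclude on a later event, a meniscal repair at surgery, it says so in the study procedures, and it has no such sentence for attendance. This stands to the extent that the entry reading is tenable. It does not remove the ambiguity, because nothing tells staff which reading to apply.

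A second reply is that the protocol nowhere says that poor attenders lose their assessments or are dropped from the analysis, and that a statistical analysis plan not at hand may define the analysis set. That is correct. A reader might infer that the protocol prescribes an analysis of good attenders only; the documents do not support that. The lettering in section 7 also passes from b to e in the text at hand, so a rule elsewhere cannot be ruled out. What remains is that the section meant for withdrawals gives no rule, although stopping and opt-out are both foreseen.

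A reader might also infer that removal would favour the BFR arm, because two of the four stopping criteria, "Numbness, tingling, paresthesias >2 hours following any BFR session" and "Nausea, severe headache, vomiting, fainting within 2 hours of BFR session", can be met only there. That inference needs several unresolved steps: the actual-attendance reading, a stop that ends all rehabilitation and not just the cuff, a stop early enough to cost four sessions, and an excess of such stops in one arm. The other two criteria, pain and instability, can occur in both arms. Different removal by arm is possible, but the documents do not establish it.

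**Conclusion.** The criterion is ambiguous, and one of its two tenable readings would damage the randomised comparison. What follows from the document is the threshold (21 of 24 sessions, failing at the fourth miss), the fact that actual failure is known only after randomisation, and the absence of a retention rule in 7(f). The range of about 2 to 15 of 70 subjects affected, and the move in detectable difference from 0.68 to about 0.77 SD at the upper end, rest on assumed attendance, independence, equal arms and conventional error rates. They apply only if the rule is used on actual attendance and, for the detectable difference, only if those subjects also leave the comparison. The size and direction of any bias cannot be determined from the protocol. This is a cheap improvement that the sponsor should make, not evidence that the trial is biased.

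**What to change.** 1. Reword the criterion in 7(b) as expected ability to attend at least 85% of the planned sessions, judged before randomisation.
2. Record actual attendance as adherence only. Do not use it to remove randomised subjects from follow-up or from the main comparison; at most it may define a supportive per-protocol analysis.
3. Replace N/A in 7(f) with a rule that a subject who stops BFR or rehabilitation stays in the assigned arm and keeps the remaining planned assessments, unless consent is withdrawn.

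The cost is an amendment to two short texts; the assessments are already planned. The downside is some effort to bring back subjects who have stopped, and a possibly smaller estimated effect because poor attenders stay in. If the entry reading was always intended, the rewording in step 1 changes nothing in practice.
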